**Table 1 Footnotes:**

Abbreviations: C-SSRS = Columbia-Suicide Severity Rating Scale; COMPASS 31 = Composite Autonomic Symptom Score; ELISA = enzyme linked immunosorbent assay; EQ-5D QOL = EuroQOL; FAP = familial amyloidotic polyneuropathy; IENFD = intraepidermal nerve fiber density; mBMI = modified body mass index; mNIS = Modified Neuropathy Impairment Score; MR = magnetic resonance; NIS = Neuropathy Impairment Score; NT-proBNP = N-terminal prohormone of B-type natriuretic peptide; NYHA = New York Heart Association; PND = polyneuropathy disability; QOL-DN = Quality of Life-Diabetic Neuropathy; R-ODS = Rasch-built Overall Disability Scale; SGNFD = sweat gland nerve fiber density; TSH = thyroid stimulating hormone; TTR = transthyretin

- Every effort should be made to perform Day 0 visit 3 weeks (±3 days) from the last dose of study drug in the parent study. However, the Day 0 visit may occur within 45 days after the last dose in the parent study. Exceptions may be made for medical or regulatory considerations only after consultation with the Medical Monitor.
- Medical history includes TTR genotype. Ongoing AEs from the parent study will be captured as Medical History on the case report form (CRF). Similarly concomitant medications that continue from the parent study will be entered into the database.
- Assessment does not need to be repeated. Information will be obtained from parent study.
- Assessment/procedure does not need to be repeated if performed during the parent study within 45 days of first dose in this study.
- mBMI will be calculated within the clinical database; this calculation does not need to be performed at the study center.
- Assessment/procedure required only if patient withdraws before the 52-week visit.
- Vital signs include blood pressure, heart rate, body temperature, and respiratory rate. Collected supine using an automated instrument after patient rests for 10 minutes. Must be performed pre-dose.
- Includes serum chemistry, hematology, and urinalysis. Refer to Section 9.1.5 for specific laboratory assessments.
- Assessment does not need to be repeated if the patient had a negative pregnancy test (urine or serum) within 14 days of the first dose.

- j. The mNIS+7 consists of the modified NIS tool (weakness and reflexes), nerve conduction studies (NCS) 5 attributes ( $\Sigma 5$ ), quantitative sensory testing (QST) by body surface area including touch pressure (TP) and heat pain (HP), and postural blood pressure. Two assessments of the mNIS+7 will be performed on separate days (1 assessment on each day). The second (repeat) assessment must be conducted at least 24 hours (approximately) but not more than 7 days after the first assessment. Each site will make every effort to have these assessments at the Week 52 visit performed by the same study personnel who performed the assessments for the patient in the patisiran study in which they were previously enrolled.
- k. The NIS+7 consists of the NIS tool (weakness, sensation, and reflexes), NCS  $\Sigma 5$ , vibration detection threshold (VDT), and heart rate response to deep breathing (HRdB). Two assessments of the NIS+7 will be performed on separate days (1 assessment on each day). The second (repeat) assessment must be conducted at least 24 hours (approximately) but not more than 7 days after the first assessment. Each site will make every effort to have these assessments at the Week 52 visit performed by the same study personnel who performed the assessments for the patient in the patisiran study in which they were previously enrolled.
- l. One assessment of the NIS will be performed at each specified visit and must be performed by a neurologist.
- m. Assessment of NIS only does not need to be repeated if done as part of the NIS+7 at the End of Study or Early Withdrawal visit or if done within the previous 26 weeks.
- n. Grip strength will be measured in triplicate using a dynamometer held in the dominant hand. Every effort will be made to use the same device for a patient throughout the duration of the study. Two assessments of the grip strength will be performed on separate days (1 assessment on each day). The second (repeat) assessment must be conducted at least 24 hours (approximately) after the first assessment, but not more than 7 days apart.
- o. Assessment does not need to be repeated if done within the previous 26 weeks.
- p. The patient will be asked to walk 10 meters. The walk must be completed without assistance from another person; ambulatory aids such as canes and walkers are permitted. The time required for the patient to walk 10 meters will be recorded. Two assessments of the 10-meter walk test will be performed on separate days (1 assessment on each day). The second (repeat) assessment must be conducted at least 24 hours (approximately) but not more than 7 days after the first assessment.
- q. Examination will include visual acuity, visual fields, and slit-lamp evaluation. An electroretinogram may also be performed, as described in Section 9.1.6
- r. Optional skin biopsies will only be obtained if the patient had skin biopsies in the parent study and has provided separate informed consent for the skin biopsies in this study. Each skin biopsy assessment will include 2 sets of tandem 3-mm skin punch biopsies (4 biopsies total), including 1 set of biopsies taken from the distal lower leg, when a patient's clinical status allows, and 1 set from the distal thigh.
- s. MR neurography will only be conducted at sites in Germany and France. In these countries, neurography may be conducted for patients who had MR neurography in the parent study and for a subset of patients providing informed consent who did not have MR neurography previously in their parent study. Patients who had imaging in the parent study should have Day 0 imaging if they did not undergo MR neurography within the past 3 months.
- t. Patients who are entering this study from a protocol that does not include the Norfolk QOL-DN questionnaire (eg, ALN-TTR02-003) do not have to complete this assessment.
- u. Patients entering this study from study ALN-TTR02-003, who were not previously participating in the cardiac subgroup, will be required to have an echocardiogram before dosing on Day 0.
- v. Serum samples for anti-drug antibodies will be collected as specified.
- w. Patisiran will be administered once every 21 ( $\pm 3$ ) days. Every effort should be made to continue dosing from the parent study in the 21 ( $\pm 3$ ) day timeframe. Doses may be administered at the clinical site or, where applicable country and local regulations allow, at home by a healthcare professional trained in the protocol.
- x. Patients who are receiving patisiran infusions at home must be contacted by the clinical site a minimum of every 30 ( $\pm 5$ ) days for assessment of adverse events and concomitant medication use. During phone contact, patients may also be asked additional questions about their general experience receiving infusions at home.

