**Table 1 Schedule of Assessments**

	Day 0 Visit	12 Week Visit	26 Week Visit	52 Week Visit	Annual Visit	End of Study	Early Withdrawal Visit
	Window ≤45 Days from Last Dose a	±4 Weeks	±4 Weeks	±4 Weeks	±6 Weeks	4 (+1) Weeks from Last Dose	4 (+1) Weeks from Last Dose
Procedure							
Informed Consent	X						
Inclusion/Exclusion Criteria	X						
Medical History	X b						
Demographics	X c						
Physical Examination	X d			X	X	X o	X o
Weight	X Prior to Each Dose					X o	X o
mBMI e	X d			X	X	X o	X o
Height	X c						
FAP Stage and PND Score	X d			X	X	X o	X o
Karnofsky Performance Status	X						
NYHA Classification	X			X			[X] f
Vital Signs g	X Prior to Each Dose						
Safety Laboratory Assessments h	X d	X	X	X	X	X	X
INR	X						
Pregnancy Test (urine)	X i		X	X	X	X	X
C-SSRS Questionnaire			X	X	X	X	X

	Day 0 Visit	12 Week Visit	26 Week Visit	52 Week Visit	Annual Visit	End of Study	Early Withdrawal Visit
	Window	≤45 Days from Last Dose a	±4 Weeks	±4 Weeks	±4 Weeks	±6 Weeks	4 (+1) Weeks from Last Dose
Procedure							
TTR Protein (ELISA)	X d		X	X	X	X	X
TSH and Vitamin A				X	X	X o	X o
Blood Sample for Long-term Storage	X	X	X	X	X	X	X
mNIS+7 j	X d			X			[X] f
NIS+7 k	X d			X			[X] f
NIS only					X l	X m	X m
Grip Strength Test n	X d			X			[X] f
10-Meter Walk Test p	X d			X			[X] f
Ophthalmology Examination q	X d			X	X	X o	X o
Skin Punch Biopsy (IENFD and SGNFD) r				X	X	X o	X o
MR Neurography s ( Germany & France only )	X		X	X	X	X o	X o
Pharmacoeconomics Questionnaire	X			X	X	X o	X o
Norfolk QOL-DN t	X d			X	X	X o	X o
COMPASS 31 Questionnaire	X d			X			[X] f
R-ODS Disability	X d			X			[X] f
EQ-5D QOL	X d			X	X	X o	X o
Echocardiogram	X d,u			X			[X] f
Troponin I and NT-proBNP	X d			X			[X] f

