### 3. INVESTIGATIONAL PLAN

#### 3.1. Overall Study Design

This is a multicenter, multinational, open-label extension study to evaluate the long-term safety and efficacy of patisiran in patients with FAP who have previously completed a patisiran study. Patients in this study will have completed “parent” study ALN-TTR02-003 or ALN-TTR02-004. Note that Study ALN-TTR02-003 is not being conducted in Japan.

Consented eligible patients will enroll in this study and receive 0.3 mg/kg patisiran IV once every 21 days for the duration of the study. All dosing visits have a window of  $\pm 3$  days. In order to maintain the every 21-day dosing schedule from the parent study, patients are expected to have their first visit (Day 0) on this study 3 weeks after their last dose visit on the parent study. However, if necessary, a patient may initiate dosing in this study up to 45 days from the time of the last dose in the parent study. Exceptions to this timing may be allowed for medical or regulatory considerations only after consultation with the Medical Monitor. The last testing visit in the parent study will serve as the baseline for this study, unless more than 45 days have elapsed, in which case the baseline tests will need to be repeated on Day 0. Eligibility for this study will be confirmed before administration of the first dose on Day 0.

The duration of the study has been determined to allow the collection of long-term safety, tolerability and efficacy data of patisiran in patients with FAP who have completed a prior study with patisiran. The estimated duration of the study is 5 years.

In order to reduce the potential for an IRR with patisiran, all patients on this study will receive premedications at least 60 minutes before the start of the patisiran infusion. Patisiran will be administered as a 70-minute IV infusion (approximately 1 mL/minute for the first 15-minutes followed by approximately 3 mL/minute for the remainder of the infusion). If the infusion duration for a patient was lengthened beyond 70 minutes due to the occurrence of an IRR while on the parent study, that infusion duration may be continued on this study for that particular patient. Returning the patient’s infusion duration to 70 minutes will require a discussion with the Medical Monitor.

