After the Day 0 visit, patients should return to the clinical site for patisiran dosing once every 21 ( $\pm 3$ ) days. Where applicable country and local regulations allow, patients may receive the patisiran infusions at home by a healthcare professional trained on the protocol and delivery of premedications and patisiran. Patients who are receiving patisiran infusions at home will have a phone contact with the site at least every 30 ( $\pm 5$ ) days. Patients will also have visits at the clinical site at approximately 12, 26 and 52 weeks, and yearly thereafter.

A complete set of efficacy assessments will be performed at 52 weeks, followed by more limited efficacy assessments yearly thereafter. In order to decrease the variability in the efficacy assessment testing at the 52-week visit, there will be a limited number of sites within any one territory that conduct these efficacy assessments (referred to as “Central Assessment Sites [CAS]”); these sites can dose and manage patients. There will also be sites that can dose and manage the patients (“Patient Care Sites [PCS]”), while sending the patients to the nearest CAS for their 52-week efficacy assessments. Every effort should be made for the patient to return to the same CAS center that the patient went to in the parent study. Yearly efficacy assessments

after the 52-week visit may be done at a PCS. Prior to starting the study, the CAS and PCS will create a delegation of responsibilities document that clearly details which site is responsible for which efficacy tests and safety parameters to ensure adherence to the protocol. This document will become part of the study site specific documentation.

Safety will be assessed throughout the study. Patients will return to the clinical site for safety evaluations at 12, 26 and 52 weeks during the first year and yearly thereafter. Patients will be continually assessed throughout the study for adverse events (AEs). Unscheduled visits for study assessments may occur if deemed necessary by the study personnel.

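### The 26-week waiver at Early Withdrawal lets a baseline value stand in for the exit FAP stage, PND, Norfolk QOL-DN and EQ-5D

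*Protocol*

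**What the plan says.** Footnote letters are those of Version 3.1 (United Kingdom). The Taiwan Version 2.1 in the same document carries the same waiver on these rows.

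- **Schedule.** In the protocol's Table 1, the rows "FAP Stage and PND Score", "Norfolk QOL-DN" and EQ-5D are marked at Day 0, Week 52, the annual visits, End of Study and Early Withdrawal. Nothing is marked at Week 12 or Week 26. Section 3.1 describes the same spacing: "A complete set of efficacy assessments will be performed at 52 weeks, followed by more limited efficacy assessments yearly thereafter".
- **Waiver at exit.** At Early Withdrawal these rows carry footnote o: "Assessment does not need to be repeated if done within the previous 26 weeks".
- **Baseline.** Footnote d says of the Day 0 assessments: "Assessment/procedure does not need to be repeated if performed during the parent study within 45 days of first dose in this study". Section 3.1 adds: "The last testing visit in the parent study will serve as the baseline for this study, unless more than 45 days have elapsed".
- **Other efficacy tests at exit.** mNIS+7, NIS+7, grip, walk, COMPASS 31, R-ODS, echocardiogram and cardiac biomarkers carry footnote f: "Assessment/procedure required only if patient withdraws before the 52-week visit". They have no 26-week waiver.
- **NIS alone.** Footnote m begins "Assessment of NIS only does not need to be repeated if done as part of the NIS+7 at the End of Study or Early Withdrawal" and also waives the exam if it was done in the previous 26 weeks.
- **Analysis.** Section 10.2.3 plans descriptive summaries of observed values and changes from baseline that include FAP stage, PND score and EQ-5D. It names no Norfolk summary. Norfolk is not collected from patients whose parent study did not use it (Section 8.1.9).

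**The concern.** A waiver for a recent assessment is sensible when that assessment was made on treatment in this study. Footnote o does not say so. For a patient who leaves in the first months, the only earlier FAP stage, PND, Norfolk or EQ-5D value is the baseline, and it may be less than 26 weeks old at the exit visit. Taken literally, the baseline then excuses the only post-baseline assessment the patient would have had.

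This sits badly with footnote f. The protocol accepts that someone who withdraws before Week 52 needs an exit value and imposes the long neurological batteries to get one, several of them performed twice on separate days. It then excuses a stage rating and two questionnaires.

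At stake are the early leavers' changes in ambulation stage and quality of life. Some of these patients are former placebo patients (Section 1.3), for whom this is the first exposure to patisiran. In a single-arm study, losing change values among people who leave because they worsen or cannot tolerate treatment would tend to make the summaries look better. No analysis plan can recover a value that was never collected.

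**Working it through.** The protocol gives no figure for missing exit data and no withdrawal rate, so there is nothing to reproduce. The check is schedule arithmetic.

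**Inputs**
- Waiver length: 26 weeks = 182 days (footnote o).
- Oldest baseline allowed at first dose: 45 days = 45/7 = 6.4 weeks (footnote d; Section 3.1).
- First scheduled post-baseline assessment of these measures: Week 52 (Table 1).
- Early Withdrawal visit: 4 (+1) weeks after the last dose (Table 1).

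**Rule.** The waiver applies when time of exit visit minus time of last assessment is at most 26 weeks. Before Week 52 the last assessment is the baseline.

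**Length of the early gap, by exit visit**
- Baseline on Day 0: up to Week 182/7 = 26.0.
- Parent-study baseline 45 days before Day 0: up to Week (182 - 45)/7 = 137/7 = 19.6.

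**The same gap, by last dose**
- 19.6 - 5 = 14.6 to 19.6 - 4 = 15.6 weeks with the oldest baseline.
- 26 - 5 = 21 to 26 - 4 = 22 weeks with a Day 0 baseline.
- Overall, a last dose at about Weeks 15 to 22. A patient dosed until Week 24 would attend at Week 28 or 29 and would have to be assessed.

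**Share of the first-year calendar inside the gap.** 19.6/52 = 38% to 26/52 = 50%. This describes the schedule and does not forecast how many patients are affected.

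**Required at an exit visit inside the gap**

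| Measure | Footnote | Post-baseline value required? |
|---|---|---|
| mNIS+7, NIS+7, R-ODS, COMPASS 31, walk, grip | f | Yes |
| FAP stage/PND, Norfolk QOL-DN, EQ-5D | o | No |

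NIS is not lost in this period, because footnote f requires NIS+7, which contains it.

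**Later withdrawals, for comparison.** Assume withdrawals spread evenly to Week 260 (5 years, Section 3.1). The waived time is the 26 weeks after each of Weeks 52, 104, 156 and 208, so 4 × 26 = 104 weeks.
- Of withdrawals after Week 52: 104/(260 - 52) = 50%.
- Of all withdrawals after Week 26: 104/(260 - 26) = 44%. After Week 19.6: 104/(260 - 19.6) = 43%.
- If follow-up stopped at Week 104: 26/(104 - 26) = 33% of those after Week 26.
- Constant withdrawal hazards of 5% to 30% per year give 50.6% to 53.7% after Week 52 and 43.6% to 44.4% after Week 26.
- Annual-visit windows of ±6 weeks move the share per interval between 26/64 = 41% and 26/40 = 65%.

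Every patient in this later group already has an on-study value no more than 26 weeks old.

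**The case against.** **Footnote o permits omission; it does not forbid the test.** This stands. A reader might infer that every early leaver gives no post-baseline value. The text supports only that none is required, and sites may still collect it.

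**Footnote o may not have been meant to cover a parent-study test.** Unlike footnotes c and d, it does not name the parent study. If only tests done in this study count, the gap closes for carried-over baselines and remains, to Week 26, for patients tested on Day 0. But Section 3.1 makes the parent test this study's baseline, footnote d lets it replace the Day 0 test, and nothing in footnote o excludes it. The ambiguity is itself a reason to clarify.

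**Early worsening is largely captured anyway.** Before Week 52 footnote f brings in neurological impairment, reported disability, autonomic symptoms, walking and grip, and reasons for withdrawal are sought (Section 4.3). This stands in part: it limits the damage but does not supply FAP stage, PND or quality of life.

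**The bias is not demonstrated.** Also fair. The protocol specifies no carry-forward, and whether an off-schedule exit value would enter a visit summary depends on windowing rules that a protocol may leave to the SAP. A value that is not collected, however, cannot enter any summary.

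**A reader might extend the point to all later withdrawals and say that half have no exit value, NIS included.** The documents do not support treating that as an error. The 50% holds only after Week 52 and under an assumed withdrawal pattern. Those patients have a recent on-study value, and a waiver of half the annual interval is an ordinary trade-off against burden.

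**Conclusion.** The point holds in a narrow form. For Early Withdrawal visits up to about Week 20 to Week 26, depending on the age of the baseline, the protocol requires no post-baseline FAP stage, PND, Norfolk QOL-DN (where the parent study used it) or EQ-5D. It does require the more burdensome footnote f tests at the same visit. Affected patients can drop out of the planned change-from-baseline summaries of FAP stage, PND and EQ-5D.

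The lower limit assumes that a 45-day-old parent-study baseline counts as an earlier assessment under footnote o. The likely direction of any effect is favourable. The number of patients and the size of the effect cannot be derived, because the document gives no withdrawal rates or timing. The study is descriptive with no powered hypothesis, so this is a cheap improvement to data collection and does not invalidate the plan. The waiver after Week 52, including NIS under footnote m, is not part of the error.

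**What to change.** For FAP stage/PND, Norfolk QOL-DN and EQ-5D in the Early Withdrawal column, state that a Day 0 or parent-study baseline value does not satisfy footnote o. These measures are then required for any withdrawal before the 52-week visit, as footnote f already does for the other efficacy tests. Under this rule the early gap falls from 19.6 to 26 weeks to zero for visits that are attended.

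The cost is one stage rating and two short questionnaires at a visit that already takes place, and one questionnaire fewer where Norfolk does not apply. The pharmacoeconomics questionnaire has the same schedule and footnote at exit. Section 10.2.5 plans only a listing of healthcare utilization data, so including it is a matter of convenience. Removing the 26-week waiver after Week 52 is optional.

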## LIST OF ABBREVIATIONS AND DEFINITIONS OF TERMS

Abbreviation	Definition
AE	adverse event
ALT	alanine transaminase
AST	aspartate transaminase
ATTR	transthyretin-mediated amyloidosis
BUN	blood urea nitrogen
CAS	Central Assessment Sites
CFR	Code of Federal Regulations
COMPASS 31	Composite Autonomic Symptom Score
CRF	case report form
CRO	clinical research organization
CYP	cytochrome P450
DLin-MC3-DMA	1,2-Dilinoleyloxy-N,N-dimethylpropylamine
DN	diabetic neuropathy
DSPC	1,2-Distearoyl-sn-glycero-3-phosphocholine
EDC	electronic data capture
ELISA	enzyme linked immunosorbent assay
EP	European Pharmacopoeia
EQ-5D	EuroQOL
EU	European Union
Σ5	5 attributes
FAC	familial amyloidotic cardiomyopathy
FAP	familial amyloidotic polyneuropathy
GCP	Good Clinical Practice
GMP	Good Manufacturing Practice
HEENT	head, ears, eyes, nose, and throat
HIPAA	Health Insurance Portability and Accountability Act of 1996
HP	heat pain
HRdb	heart rate response to deep breathing

Abbreviation	Definition
IB	Investigators Brochure
ICF	informed consent form
ICH	International Conference on Harmonization
IEC	Independent Ethics Committee
IENFD	intraepidermal nerve fiber density
INN	International Nonproprietary Name
INR	international normalized ratio
IRB	Institutional Review Board
IRR	infusion-related reaction
IRS	interactive response system
IUD	intrauterine device
IUS	intrauterine system
IV	intravenous
LNP	lipid nanoparticle
mBMI	modified body mass index
MedDRA	Medical Dictionary for Regulatory Activities
mNIS	Modified Neuropathy Impairment Score
mRNA	messenger RNA
MR	magnetic resonance
NCS	nerve conduction studies
NHP	non-human primate
NIS	Neuropathy Impairment Score
NIS-W	Neuropathy Impairment Score- Weakness
NSAID	nonsteroidal anti-inflammatory drug
NT-proBNP	N-terminal prohormone of B-type natriuretic peptide
NYHA	New York Heart Association
OTC	over-the-counter
PCS	Patient Care Sites
PD	pharmacodynamic

Abbreviation	Definition
PEG 2000 -C-DMG	(R)-methoxy-PEG 2000 -carbamoyl-di-O-myristyl-sn-glyceride
PK	pharmacokinetic
PND	polyneuropathy disability
PO	per os (orally)
QOL	quality of life
QOL-DN	Quality of Life-Diabetic Neuropathy
QST	quantitative sensory testing
RBC	red blood cell
RBP	retinol binding protein
RNAi	ribonucleic acid interference
R-ODS	Rasch-built Overall Disability Scale
SAE	serious adverse event
SGNFD	sweat gland nerve fiber density
siRNA	small interfering ribonucleic acid
SUSAR	Suspected Unexpected Serious Adverse Reaction
TP	touch pressure
TSH	thyroid stimulating hormone
TTR	transthyretin
TUDCA	tauroursodeoxycholic acid
ULN	upper limit of normal
USP	United States Pharmacopeia
V30M	Val30Met
VDT	vibration detection threshold
WBC	white blood cell
WT	wild type

